7.4.3.3 Missing Data

Missing values of atrophic acne scar counts will be imputed using MI (Multiple Imputation) under the Missing At Random (MAR) assumption. It is expected that the pattern of missing data will be monotonic, with slight deviations being corrected by the Markov Chain Monte Carlo (MCMC) method of the MI procedure.

Missing values of acne lesion counts, SGA scores and IGA scores will be imputed using Last Observation Carried Forward (LOCF). Moreover, for binary endpoints Missing as Failure (MAF) method will be used as additional analysis.

For the sensitivity analyses of the primary endpoint, missing data will be imputed using a Jumpto-Reference (J2R) approach under the Missing Not At Random (MNAR) assumption and Last Observation Carried Forward (LOCF).

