### 4 SAMPLE SIZE CONSIDERATION

The sample size calculation is based on the results of the study RD.06.SPR.118295 "A Multi-Center Study to evaluate Subject Reported Outcomes with use of trifarotene 50  $\mu$ g/g cream in the treatment of moderate facial and truncal acne vulgaris" and of the study RD.03.SPR.105061 "Effect of Adapalene 0.3% - Benzoyl Peroxide 2.5% gel versus vehicle gel on the risk of formation of atrophic acne scars in moderate to severe acne subjects".

In study RD.06.SPR.118295, the following results were obtained for the absolute change from baseline in total atrophic acne scar count at week 24:

These results refer to a whole face treatment whilst in the current study a split-face design is used. Moreover, due to the lack of a Vehicle arm, it is not possible to estimate the mean value and the variability of the difference in mean absolute change from baseline in total atrophic acne scar between treatment arms.

It is possible to hypothesize that the mean reduction in trifarotene 50  $\mu$ g/g cream arm when only half-face is treated is -1.7 but there are no data for estimating the variability of the difference between trifarotene 50  $\mu$ g/g cream and vehicle cream.

In study RD.03.SPR.105061 a split-face design was used and the following results were obtained for the absolute change from baseline in total atrophic acne scar count at week 24:

CCI

Under the following hypotheses:

- Mean absolute change from baseline in total atrophic acne scar count at week 24 for trifarotene 50 μg/g cream is -1.7
- Mean absolute change from baseline in total atrophic acne scar count at week 24 for Vehicle cream is zero
- Difference absolute change from baseline in total atrophic acne scar count at week 24 between trifarotene 50 μg/g cream and vehicle cream is -1.7
- Variability of the difference between trifarotene 50 μg/g cream and vehicle cream is 6.0 (derived by supposing an increase of about 35% of the variability observed in study RD.03.SPR.105061)

the sample size for a Student's t-test for paired samples can be calculated according to the following formula:

$$n \ge \frac{\left(t_{\frac{1-\alpha}{2},n-1} + t_{1-\beta,n-1}\right)^2 \sigma_{Diff}^2}{\left(\mu_{Trifarotene} - \mu_{Vehicle}\right)^2}$$

where  $t_{p,v}$  is the Student's t distribution quantile with v degrees of freedom and probability p (n is rounded up to the closest integer).

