**Table 8 Sample Size Calculation** 

α (2-sided)	β	Power (%)	μ Trifarotene - μ Vehicle	♂ Diff	n	Drop-out and Non-evaluable Proportion (%)	Subjects to be Randomized
0.05	0.2	80	-1.7	6.0	100	15	118

An initial number of 118 subjects is planned to be randomised. Due to the uncertainty of the estimation of the variability, a blinded sample size re-estimation will be performed after 40 subjects complete/discontinue the study (i.e. after 33% of the initial planned subjects complete/discontinue the study) in order to evaluate the need for additional subjects to be randomized.

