### 6.1.5 Statistical Tests and Confidence Intervals

A two-sided type I error  $\alpha = 0.05$  will be used to declare statistical significance for the primary endpoints and the secondary endpoints. Confidence intervals (CIs) will be two-sided with 95% coverage for the primary endpoint and the secondary endpoints. The following flagging conventions will be applied for the p-values of all statistical testing:

- $0.01 \le \text{p-values} < 0.05 \text{ will be flagged with one asterisk (e.g. "0.0499 *")}$
- $0.001 \le \text{p-value} \le 0.01$  will be flagged with two asterisks (e.g. "0.0099 \*\*")
- $0.0001 \le \text{p-value} < 0.001 \text{ will be flagged with three asterisks (e.g. "0.0009 ***")}$
- p-value < 0.0001 will be flagged with four asterisks (e.g. "< 0.0001 \*\*\*\*")

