### 6.3.3 Analysis of Primary Endpoint

The hypothesis test for the primary endpoint can be formally defined as follows:

$$\begin{cases} H_0: \mu_{Diff} = 0 \\ H_a: \mu_{Diff} \neq 0 \end{cases}$$

where  $\mu_{Diff}$  is the mean of the differences in change from baseline in total atrophic acne scar count at Week 24 between the trifarotene 50  $\mu$ g/g side and the vehicle side.

The hypothesis test for the primary endpoint will be evaluated on the ITT population at the two-sided significance level  $\alpha = 0.05$ . Efficacy will be claimed if the between treatment difference on the primary endpoint is statistically significant with a p-value < 0.05.

The bilateral difference between the trifarotene side and the vehicle side in absolute change from baseline in total atrophic acne scar counts at Week 24 will be analyzed on the ITT population using the Student's t-test for paired samples. The point estimate of the mean difference and the related 95% confidence interval will be presented. Assumption of normality will be checked. If normality assumption is not met, the appropriate non-parametric statistical method (Wilcoxon signed rank test, Hodges-Lehmann estimate of location shift and asymptotic confidence interval) will be used.

For analysis of change from baseline in total atrophic acne scar counts to Week 24, missing counts will be imputed using Multiple Imputation (MI) under the Missing At Random (MAR) assumption. It is expected that the pattern of missing data will be monotonic, with slight deviations being corrected by the Markov Chain Monte Carlo (MCMC) method of the SAS MI procedure. Separate imputations by treatment group will be carried out. Linear regression will be employed to model the missing acne counts, with the following covariates included in the imputation model: non-missing total atrophic acne scar counts from earlier time points (see Section 6.3.6.2 for further details).

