As sensitivity analysis of the primary endpoint, the primary analysis will be repeated on the ITT population by imputing atrophic acne scar counts on the basis of a Jump-to-Reference (J2R) approach under the Missing Not At Random (MNAR) assumption. Missing values of bilateral difference in atrophic acne scar counts between the trifarotene side and the vehicle side will be imputed as zero (0).

As additional sensitivity analysis of the primary endpoint, the primary analysis will be repeated on the ITT population by imputing missing data using Last Observation Carried Forward (LOCF). In case no post-baseline value is available, baseline value will be carried forward.

Missing values of acne lesion counts, SGA scores and IGA scores will be imputed using LOCF. In case no post-baseline value is available, baseline value will be carried forward. SGA/IGA success will be calculated from the imputed ordinal SGA/IGA scores. Moreover, SGA/IGA success will be imputed using Missing as Failure (MAF) method as additional analysis.

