### 6.3.6.5 Multiple Comparison/Multiplicity

In order to maintain the overall type I error rate at 0.05, a predefined hierarchal testing procedure will be implemented.

The hypothesis test for the primary endpoint will be evaluated on the ITT population at the significance level  $\alpha = 0.05$ .

Approved

The hypothesis tests for the scar secondary efficacy endpoints will be evaluated on the ITT population according to the following predefined order, all at the same significance level  $\alpha = 0.05$ , moving to the next hypothesis test only after a success on the previous hypothesis test.

- 1) Absolute change from Baseline in total atrophic acne scar count at Week 20
- 2) Absolute change from Baseline in total atrophic acne scar count at Week 16
- 3) Absolute change from Baseline in total atrophic acne scar count at Week 12
- 4) Absolute change from Baseline in total atrophic acne scar count at Week 8
- 5) Absolute change from Baseline in total atrophic acne scar count at Week 4
- 6) Absolute change from Baseline in total atrophic acne scar count at Week 2
- 7) Absolute change from Baseline in total atrophic acne scar count at Week 1

This approach does not inflate the Type I error rate as long as the hypothesis tests for the secondary efficacy endpoints are conditional on the success of the primary, there is a prospective specification of the testing sequence and no further testing is performed once the sequence breaks, that is, further testing stops as soon as there is a failure of a hypothesis test in the sequence to show significance at the predefined alpha level.

No hypothesis test will be evaluated for the rest of the secondary efficacy endpoints. p-values and 95% confidence intervals will be presented for descriptive purposes only.

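### LOCF as the main method for missing acne lesion counts, SGA and IGA can bias the Week 24 side difference in either direction; multiple imputation, already planned for scar counts, should take its place

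*SAP*

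**What the plan says.** SAP 6.3.6.2: "Missing values of acne lesion counts, SGA scores and IGA scores will be imputed using LOCF". Protocol 7.4.3.3 has the same rule: "Missing values of acne lesion counts, SGA scores and IGA scores will be imputed using Last Observation Carried Forward (LOCF"). The SAP adds that baseline is carried forward if a subject has no post-baseline value, and that SGA/IGA success is calculated from the imputed scores. Missing as Failure is an additional analysis of that binary success.

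For atrophic scar counts the same SAP section specifies MI under missing at random: 50 imputations, linear regression on earlier counts, minimum 0, integer rounding, predictive mean matching as fallback, and pooling across imputations. SAP 6.3.4 lists LOCF for the primary endpoint only as a sensitivity analysis, beside jump-to-reference, observed case and per protocol.

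Only scar counts are in the testing hierarchy of SAP 6.3.6.5. For the remaining secondary endpoints, "p-values and 95% confidence intervals will be presented for descriptive purposes only". The passages that define the lesion, SGA and IGA endpoints and their tests are blacked out.

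**The concern.** The plan treats LOCF as second best for scar counts and as the main method for three other efficacy measures, and the visible text gives no reason. Two features of this trial make LOCF a poor fit.

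- Effects develop over time. Protocol 5.2 regards 12 weeks as enough to judge acne lesions and adds 12 more to follow later outcomes. A subject who leaves early contributes a value near baseline as if it were a Week 24 result.
- Withdrawal can depend on the outcome. Protocol 5.3.4 and SAP 3.2.4 let the investigator withdraw a subject for dramatic differences between the two sides. LOCF then fixes that large difference at Week 24.

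The first pulls the estimated side difference towards zero and the second pushes it away, so a reader of the results could not tell the sign of the error. A single carried-forward value also adds no uncertainty for being missing. At stake is the accuracy of supportive results on acne and scar severity, not the primary conclusion.

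**Working it through.** **The plan's own figure.** SAP Table 8 gives "0.05 0.2 80 -1.7 6.0 100 15 118": alpha, beta, power (%), difference, SD, evaluable n, drop-out and non-evaluable (%), number randomised. With the SAP Section 4 formula, (1.984 + 0.845)² × 6.0² / 1.7² ≈ 99.7, so n = 100 (power 80.1%), and 100 / 0.85 = 117.6, so N = 118. This reproduces. It concerns scar counts; the documents give no effect, SD or trajectory for lesion counts, SGA or IGA, so everything below rests on assumptions.

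**Step 1: bias towards zero.** Let d be the share of subjects whose value is carried forward, and f the average fraction of the Week 24 side difference already present at their last value. If drop-out is unrelated to outcome, LOCF keeps (1 − d) + d × f. Take d = 15% from Table 8; that figure also includes non-evaluable subjects. Observation at every scheduled visit is assumed.

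| Drop-out timing (assumed) | Linear growth to Week 24 | Plateau from Week 12 |
|---|---|---|
| Last value equally likely at baseline, Weeks 1, 2, 4, 8, 12, 16, 20 | f = (63/8)/24 = 0.328; keeps 90% | f = 4.25/8 = 0.531; keeps 93% |
| Even over calendar time, last scheduled visit used | f = 245/576 = 0.425; keeps 91% | f = 16.42/24 = 0.684; keeps 95% |
| Even over calendar time, full assessment at exit | f = 0.5; keeps 92.5% | f = 0.75; keeps 96% |

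The limits at d = 15% are 85% (f = 0) and 100% (f = 1). At an assumed d of 5% they are 95% and 100%; at 25%, 75% and 100%, and the first row becomes 83% and 88%.

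**Step 2: direction under two drop-out mechanisms.** This was an illustrative simulation: 500 runs, N = 118, true Week 24 difference −1.7, SD 6 and visit-to-visit correlation 0.8 (scar-count planning values and an assumed correlation, borrowed for want of others), nominal 15% drop-out, 20 imputations. Entries are mean estimate, with 95% interval coverage in brackets.

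| Drop-out | Trajectory | LOCF | MI | Observed case |
|---|---|---|---|---|
| Random | Linear | −1.56 (94%) | −1.72 (95%) | −1.72 |
| Random | Plateau Week 12 | −1.65 (94%) | −1.76 (95%) | −1.76 |
| Random | Flat | −1.67 (94%) | −1.67 (95%) | −1.67 |
| More likely after a large observed difference | Linear | −2.04 (89%) | −1.72 (94%) | −1.25 |
| Same | Plateau Week 12 | −2.08 (90%) | −1.69 (96%) | −1.19 |
| Same | Flat | −2.26 (83%) | −1.70 (96%) | −1.20 |

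Monte Carlo error of each mean is about 0.6/√500 = 0.03. Realised drop-out was not recorded in the last three rows, so read those for direction only. The simulation imputes the side difference directly, whereas the SAP imputes each side separately, so it compares the principles and does not evaluate the SAP's exact procedure.

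**Step 3: standard error.** Counting 118 subjects as observed instead of about 100 gives √(100/118) = 0.92 of the completers' standard error, about 8% smaller. The simulation agrees: 0.552 for LOCF against 0.597 for MI (random drop-out, linear case).

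**The case against.** Four arguments on the other side have force.

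- **Direction.** A reader might infer that LOCF is bound to understate the side difference. The documents do not support that. They give no trajectory for these measures, Protocol 5.2 points to an early plateau for lesions, a flat difference with random drop-out leaves LOCF unbiased, and asymmetry-driven withdrawal reverses the sign. This stands: the bias is possible, not certain, and its direction is open.
- **Uncertainty.** A reader might infer that LOCF intervals are far too narrow. In the random drop-out runs the LOCF standard error matched that estimator's own spread (0.552 against 0.548 in the linear case) and coverage was about 94%. The larger coverage losses came mainly from bias.
- **Scope and reporting.** A reader might infer that all other efficacy measures are affected, or that these three will certainly carry p-values. The LOCF rule names only lesion counts, SGA and IGA; subject-reported outcomes get an observed-case summary without imputation (SAP 6.3.2). The sentence on descriptive p-values concerns remaining secondary endpoints, and the visible secondary endpoints are all scar counts. How the other three are tested is hidden.
- **Mitigation.** Protocol 5.5.1 asks for a full assessment at early termination, which brings the last value close to exit and gives the milder figures in Step 1. Missing as Failure adds a second look at SGA/IGA success.

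None of this removes the point. Missing as Failure leaves lesion counts and ordinal scores uncovered, and no visible alternative can be confirmed for them.

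**Conclusion.** The point holds in a limited form. LOCF is the main method for three supportive efficacy measures although the plan already prefers MI for scar counts, and it can move their Week 24 side difference either way. At 15% drop-out it keeps about 90% to 96% of a difference that grows linearly to Week 24 or plateaus at Week 12, depending on drop-out timing. It overstates the difference if marked asymmetry drives withdrawal; the size of that effect is not established. Its standard error is roughly 8% smaller than with MI. All of these figures rest on assumed trajectories, drop-out patterns and variances, because the documents give none for these measures. Primary inference, the sample size of 118 and the type I error hierarchy are not affected. This is a worthwhile refinement, not a flaw in the trial's main conclusion.

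**What to change.** In SAP 6.3.6.2:

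- Make MI under missing at random the main method for acne lesion counts. The scar-count procedure, with its minimum of 0 and integer rounding, transfers.
- Impute SGA and IGA scores with an ordinal logistic model or predictive mean matching, and derive success from the imputed scores. The linear-regression model for scar counts does not carry over directly to ordinal scores.
- Keep LOCF and Missing as Failure as sensitivity analyses. Observed case alone would not do as the main method: in the asymmetry-driven runs it was biased towards zero.
- Because Protocol 7.4.3.3 also states LOCF, document and justify the change under SAP Section 7.

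The cost is SAP wording, modest programming and a separate imputation model for the ordinal scores. Sample size and the primary test stay as they are.

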### 6.3.6.3 Interim Analyses and Data Monitoring

No interim analysis will be performed. A blinded sample size re-estimation will be performed after 40 subjects complete/discontinue the study (i.e. after  $\sim$ 33% of the initial planned subjects complete/discontinue the study) in order to evaluate the need for additional subjects to be randomized (see Section 4.1).

### **6.3.6.4** Multicenter Study

No analysis by center is planned for this study.

### 6.3.6.5 Multiple Comparison/Multiplicity

In order to maintain the overall type I error rate at 0.05, a predefined hierarchal testing procedure will be implemented.

The hypothesis test for the primary endpoint will be evaluated on the ITT population at the significance level  $\alpha = 0.05$ .

Approved

The hypothesis tests for the scar secondary efficacy endpoints will be evaluated on the ITT population according to the following predefined order, all at the same significance level  $\alpha = 0.05$ , moving to the next hypothesis test only after a success on the previous hypothesis test.

- 1) Absolute change from Baseline in total atrophic acne scar count at Week 20
- 2) Absolute change from Baseline in total atrophic acne scar count at Week 16
- 3) Absolute change from Baseline in total atrophic acne scar count at Week 12
- 4) Absolute change from Baseline in total atrophic acne scar count at Week 8
- 5) Absolute change from Baseline in total atrophic acne scar count at Week 4
- 6) Absolute change from Baseline in total atrophic acne scar count at Week 2
- 7) Absolute change from Baseline in total atrophic acne scar count at Week 1

This approach does not inflate the Type I error rate as long as the hypothesis tests for the secondary efficacy endpoints are conditional on the success of the primary, there is a prospective specification of the testing sequence and no further testing is performed once the sequence breaks, that is, further testing stops as soon as there is a failure of a hypothesis test in the sequence to show significance at the predefined alpha level.

No hypothesis test will be evaluated for the rest of the secondary efficacy endpoints. p-values and 95% confidence intervals will be presented for descriptive purposes only.

### 6.3.6.6 Use of an Efficacy Subset of Subjects

The classification of the protocol deviations and the exclusion of subjects from the Per Protocol (PP) population will be determined prior to breaking the study blind (see Section 5.2).

The analysis on the PP population will allow evaluating the impact of major protocol deviations on the estimation of the treatment effect.

### 6.3.6.7 Active-Control Studies Intended to Show Equivalence

Not applicable.

### **6.3.6.8** Examination of Subgroups

No subgroup analysis is planned for this study.

### **6.3.6.9** Analysis Visits Definition

Efficacy and safety by-visit summaries and analyses will use analysis visits. Both scheduled and unscheduled visits (including early termination visit) will be windowed based on the following analysis visit windows.

_	-
- (	_)
- 2	к
- (	נו
- 2	_
	>
-	5
	7
- 2	
- 5	₹
č	5
2	5
2	5
2	5
\nn	

Analysis Visit	Target Study Day	Analysis Visit Window
Baseline	1	<= 1
Week 1	8	4 - 11
Week 2	15	12 - 19
Week 4	29	22 - 36
Week 8	57	50 - 64
Week 12	85	75 - 95
Week 16	113	103 - 123
Week 20	141	131 - 151
Week 24	169	>= 159

If two or more assessments (include both scheduled and unscheduled assessments) are available for the analysis visits then all assessments will be listed and the following rules will be applied for determining the values to be used for the summaries and analyses.

- Efficacy assessments: the assessment taken closest to the target study day will be used for the summaries and analyses;
- Safety assessments, excluding clinical laboratory tests: the assessment taken closest to the target study day will be used for the summaries and analyses;
- Clinical laboratory tests: the latest assessment will be used for the summaries and analyses.

### 6.4 Safety Analysis

### 6.4.1 Extent of Exposure

The mean daily amount of drug applied will be calculated as the difference between the weight (in grams) of dispensed pumps and the weight (in grams) of returned pumps (missing pumps not returned by the subjects are assigned a weight difference of 45.0 grams for US sites and 75.0 grams for EU and Canada sites - the nominal fill weight of drug - for the aim of this calculation, supposing their content was completely used) divided by the number of days of use of the pumps (calculated as the difference between the date of compliance assessment and the dispensing date of each pump). The date of compliance assessment will be used instead of the actual pumps return date in order to avoid an overestimation of the number of days of use in case of delayed return of the pumps and to estimate the number of days of use in case of pumps not returned. Small differences (up to 0.5 g) between weights of dispensed and returned pumps are deemed due to weighting errors and thus are ignored and handled as no differences.

The mean daily amount of drug applied will be listed and summarized at each analysis visit using descriptive statistics (n, mean, standard deviation, median, first and third quartile, min and max) by treatment side in the Safety population.

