Sponsor Request:	An indication that the study subject was removed from the study
	at the sponsor's request.
Other ^a :	This category is to be used for a subject who discontinues due to a
	reason other than as specified in the predefined categories above.
	Explain the reason for discontinuation in the comment section of
	the Exit Form.

^a If reason for discontinuation is "withdrawal by subject", "withdrawal by parent/guardian", "physician decision" or "other", the subject will be questioned to rule out the possibility of an AE (this should be documented in the comment section of the Exit Form).

^b Investigator may withdraw a subject for dramatic, clinically significant differences in appearance between the right and left sides of the face where full face treatment may be indicated, based on the investigator's clinical judgment.

The reason(s) for withdrawal will be documented in the CRF. Subjects who have been randomized will not be replaced by another subject.

Subjects who prematurely discontinue study drug will be encouraged to complete the scheduled study visits for safety purposes and for collecting at least the data for the primary endpoint, before study exit.

When a subject discontinues the study, he/she will be fully assessed whenever possible, and followed according to guidelines presented in Section 5.5.1 - Early Termination Visit.

Reasonable efforts will be made to contact subjects who are lost to follow-up (e.g., non-response/contact after 2 phone calls and a certified letter with return receipt). These efforts must be documented in the subject's file.

The Sponsor has the right to terminate the study at any time in case of SAEs or if special circumstances concerning the investigational product or the company itself occur, making further treatment of subjects impossible. In this event, the investigator(s) will be informed of the reason for study termination.

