5.4.8 Dose Modification

If a subject experiences persistent skin dryness or irritation, the Investigator may consider a reduced application frequency for the study drug in the first 4 weeks of the study, for a maximum duration of 2 weeks. In such cases, the treatment on each CCI should be reduced in a similar fashion, even if the irritation is only on one CCI

Subjects should be instructed to capture all missed applications in the dosing calendar. Sites will record the timing and details of a prescribed dose reduction for topical medication in source records.

Signs and symptoms of local cutaneous irritation will be considered as Adverse Events if they are severe enough to lead to permanent discontinuation of study drug or if they require the use of concomitant treatment including OTC products (other than moisturizers). Refer to Section 6.11.1 for further details on local tolerability assessment.

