Study Terminated by Sponsor:	An indication that the clinical study was stopped by its sponsor.
Sponsor Request:	An indication that the study subject was removed from the study at the sponsor's request.
Other a :	This category is to be used for a subject who discontinues due to a reason other than as specified in the predefined categories above. Explain the reason for discontinuation in the comment section of the Exit Form.

- a) If reason for discontinuation is "withdrawal by subject", "withdrawal by parent/guardian", "physician decision" or "other", the subject will be questioned to rule out the possibility of an AE (this should be documented in the comment section of the Exit Form).
- b) Investigator may withdraw a subject for dramatic, clinically significant differences in appearance between the right and left sides of the face where full face treatment may be indicated, based on the investigator's clinical judgment.

The reason(s) for withdrawal will be documented in the CRF. Subjects who have been randomized will not be replaced by another subject.

Subjects who prematurely discontinue study drug will be encouraged to complete the scheduled study visits for safety purposes and for collecting at least the data for the primary endpoint, before study exit.

When a subject discontinues the study, he/she will be fully assessed whenever possible, and followed according to guidelines presented in section 3.4.1.

Reasonable efforts will be made to contact subjects who are lost to follow-up (e.g., non-response/contact after 2 phone calls and a certified letter with return receipt). These efforts must be documented in the subject's file.

The Sponsor has the right to terminate the study at any time in case of SAEs or if special circumstances concerning the investigational product or the company itself occur, making further treatment of subjects impossible. In this event, the investigator(s) will be informed of the reason for study termination

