### 3.3.5 Treatment Compliance - Primary Source Data

Subjects will be instructed by study personnel on the importance of being compliant with the use of the study drug and non-study products.

Subjects will receive an electronic tablet at baseline for recording study medication use on each half-face (electronic dosing calendar) with clear instructions for daily use throughout the study (see Section 3.1.2). The subject-reported data in the dosing calendar will be used as the primary source data for calculating treatment compliance, per each half-face.

Results are uploaded to a secure portal for remote monitoring, with subject counseling, as needed, throughout the study.

Subjects will be instructed to return the study electronic tablet and all study medication at each study visit. Site personnel will review dosing compliance data since the last visit, derive treatment compliance for each half-face and counsel/re-train subjects, if needed. Treatment compliance will be derived from the total expected doses and number of actual doses recorded, over a given visit interval.

Any missed dose will be considered a protocol deviation, based on recordings in the dosing calendar. Subjects should be appropriately counseled on the importance of following study drug dosing instructions and daily recordings in the dosing calendar. Subjects should be reminded and encouraged to follow guidelines for non-study product use, throughout the study.

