### **6.2.7 Measurements of Treatment Compliance**

### **6.2.7.1** Study Duration and Treatment Duration

For randomized subjects who discontinued before treatment, study duration will be calculated as date of end of participation minus date of randomization plus one (1).

For randomized subjects who underwent treatment, study duration will be calculated as date of end of participation minus date of first treatment plus one (1).

Study duration will be summarized for all patients in the ITT population using descriptive statistics (n, mean, standard deviation, median, first and third quartile, min and max).

Treatment duration will be calculated as date of last treatment minus date of first treatment plus one (1) and will be summarized using descriptive statistics (n, mean, standard deviation, median, first and third quartile, min and max) by treatment side (trifarotene 50  $\mu$ g/g versus vehicle) and overall in the ITT population.

Listings presenting study duration and treatment duration will be provided.

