### 6.2.7.3 Prescribed Dose Reductions

Descriptive statistics (n, mean, standard deviation, median, first and third quartile, min and max) or frequencies and proportions (n, %) of subjects for each classification category (as applicable) will be presented at each analysis visit for drugs in the ITT population for the following:

- Subjects with Prescribed Dose Reduction since the Last Scheduled Visit
- Reasons for Prescribed Dose Reduction
- Application/Dose Frequency during the Prescribed Dose Reduction
- Duration of Prescribed Dose Reduction (days)
- Missed Applications due to Prescribed Dose Reductions

Duration of the prescribed dose reduction will be calculated as Dose Reduction End Date minus Dose Reduction Start Date plus one (1).

Listings for drugs prescribed dose reductions will be provided.

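### SAP 6.4.1 counts days after a permanent stop as days of pump use, so for returned pumps the mean daily amount is understated in the interval in which a subject stops

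*SAP*

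**What the plan says.** The mean daily amount in SAP 6.4.1 is the weight difference between dispensed and returned pumps over a denominator given as "number of days of use of the pumps (calculated as the difference between the date of compliance assessment and the dispensing date of each pump". Section 6.4.1 explains that it prefers this date to the actual return date "in order to avoid an overestimation of the number of days of use in case of delayed return of the pumps", and also to have an end date when a pump never comes back. An unreturned pump is treated as emptied: 45 g at US sites, 75 g at EU and Canadian sites. The result is listed and summarised descriptively by analysis visit and treatment side in the Safety population.

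Three other places bear on the denominator:

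- SAP 3.3.5 ties the compliance review to study visits: "Site personnel will review dosing compliance data since the last visit, derive treatment compliance for each half-face".
- SAP 3.2.4, like Protocol 5.3.4, expects attendance to go on after a stop: "Subjects who prematurely discontinue study drug will be encouraged to complete the scheduled study visits".
- SAP 6.2.7.1 already uses the last treatment date: "Treatment duration will be calculated as date of last treatment minus date of first treatment plus one (1".

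Section 6.4.1 does not refer to the last treatment date, and no other section corrects its definition.

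**The concern.** A pump loses weight only while cream is being applied. If a subject stops for good partway through an interval and comes back at the next scheduled visit, the weight loss stops growing at the last application, but the day count runs on to the visit. The days in between are then labelled days of use, although the drug was not in use. That defeats the aim stated in the same section.

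The subjects affected are ones whose exposure a safety reader may look at closely. Related cutaneous adverse events leading to permanent discontinuation are a predefined event of special interest (Protocol 6.11.2.1.3). In the listing, such a subject could seem to have applied much less per day of use than was the case. Section 6.4.1 is the only planned summary of grams applied per side.

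**Working it through.** The documents give no exposure figure, so there is none to reproduce. The check is on the definition.

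**Inputs**

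- Denominator: compliance assessment date minus dispensing date, nothing subtracted (SAP 6.4.1).
- Compliance assessment date: not defined. It is read here as the visit date, from SAP 3.3.5.
- Dispensing interval: 4 weeks, or 28 days (Protocol 5.4.5: Baseline and Weeks 4, 8, 12, 16 and 20).
- Visit targets: Week 1 = Day 8, Week 2 = Day 15, Week 4 = Day 29, Week 8 = Day 57 (SAP 6.3.6.9).
- Stop dates: not in the documents, so assumed. The amount per application is taken as constant.

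**Formula**

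Let L be the days from dispensing to compliance assessment, and d the days from dispensing through the last application, with daily dosing until then. Then

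SAP value / amount per day up to the stop = d / L, and understatement = 1 − d / L.

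**A stop in a 28-day interval**

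| d | d / L | Understatement | Factor to correct |
|---|---|---|---|
| 7 | 7/28 = 0.25 | 75% | 4.0 |
| 14 | 14/28 = 0.50 | 50% | 2.0 |
| 21 | 21/28 = 0.75 | 25% | 1.33 |

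**A stop in the first 4 weeks**

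The Week 1 and Week 2 visits shorten the span after the stop. Take a stop after 10 dosing days, Days 1 to 10. The next visit is Week 2, Day 15.

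- Counting from Baseline dispensing: L = 15 − 1 = 14 and 10/14 = 0.71, so 29% low.
- If re-dispensing at Week 1 restarts the count, which the SAP does not say: L = 15 − 8 = 7, d = 3 and 3/7 = 0.43, so 57% low.

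In both cases 4 days are wrongly counted.

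**Does the cap work?**

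Take a pump dispensed on Day 29, last used on Day 35 and assessed on Day 57. The present denominator is 57 − 29 = 28. The capped one is min(57, 35 + 1) − 29 = 7, which is the number of dosing days. For a subject who applies up to the evening before the visit, the last treatment date plus one is the visit date and nothing changes.

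**Unreturned pumps**

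Over 28 days, an unreturned pump gives 45/28 = 1.61 or 75/28 = 2.68 g/day whatever was used. Capping such a pump at a 10-day stop would give 75/10 = 7.5 g/day, which enlarges an assumed amount. The cap should therefore apply to returned pumps only.

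**Rough effect on a by-visit mean**

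If a share f of contributing subjects stop in an interval, on average midway, the mean falls by about f × 50%. The planning allowance of 15% for drop-out and non-evaluable subjects (SAP section 4) is not a stopping rate, but it gives a scale. Spread evenly over six intervals, f = 15%/6 = 2.5% and the shift is about 1.25%. All in one interval, it is 15% × 50% = 7.5%.

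**The case against.** The strongest reply is that a mean daily amount over calendar days is a legitimate measure, and that section 6.4.1 never promises an amount per treated day. That stands as far as the measure goes. It does not rescue the label: the section calls its denominator days of use and sets out not to overestimate it, and days after a permanent stop are not days of use.

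The permanent-stop reading also depends on an undefined term. If the compliance assessment date were set to the last dose, the problem would disappear. SAP 3.3.5 points to the visit, but this remains an assumption. Subjects who leave the study should have an Early Termination assessment (SAP 3.4.1), which can shorten the span for them.

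A reader might go further in three ways that the documents do not support.

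- **Prescribed reductions.** Protocol 5.4.8 allows a "reduced application frequency for the study drug in the first 4 weeks of the study, for a maximum duration of 2 weeks", and SAP 6.2.7.2 removes those omissions from the compliance denominator. One might infer that 6.4.1 must do the same. But compliance asks whether instructions were followed, and exposure asks how much was applied. A subject told to apply less often does receive less per day. Both half-faces are to be reduced alike, so the ratio between sides is about unchanged, and SAP 6.2.7.3 separately tabulates "Missed Applications due to Prescribed Dose Reductions".
- **The whole table is biased low.** Counting unreturned pumps as fully used can push the mean up, so the net direction is not known.
- **Larger early losses.** Assessing a stop after 10 days only at Day 29 gives 10/28, or 64% low. That skips the Week 2 visit, at which drug is to be returned and compliance reviewed.

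**Conclusion.** The point holds as a small correction to one descriptive safety output. For returned pumps, SAP 6.4.1 counts days after a permanent stop as days of use and so understates the mean daily amount in the interval of the stop: by 75%, 50% or 25% for assumed stops after 7, 14 or 21 of 28 days. In the first 4 weeks the extra visits leave fewer days to be miscounted. Individual listed values can be well off, while the shift in a by-visit mean depends on how many subjects stop, which the documents do not give. The conclusion rests on the compliance assessment date being the visit date and on a constant amount per application. The primary analysis, the sample size and all efficacy inference are untouched.

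**What to change.** In SAP 6.4.1:

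1. For returned pumps, define days of use as min(compliance assessment date, date of last treatment + 1) minus dispensing date.
2. Set zero or negative results to missing. They arise when a pump is dispensed after the last application.
3. Leave the rule for unreturned pumps as it is.
4. State that the compliance assessment date is the visit date, if that is what is meant.
5. Keep days omitted under a prescribed reduction in this main measure.

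The cap does not remove a temporary interruption followed by resumption, such as one while a re-challenge result is awaited. If that matters, an optional second line can give the amount per applied day, using the applications recorded in the dosing calendar.

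The cost is a short addition to the text and one extra derivation from dates already needed for 6.2.7.1. If the calendar-day average is still wanted, it needs its own line and label.
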